## 10 Assessment of Safety and Data Safety Monitoring Plan (DSMP)

### 10.1 Definitions

The following definitions will be used in the assessment of safety:

*Adverse Event (AE)* is any untoward or unfavorable medical occurrence in a human subject, including any abnormal sign (for example, abnormal physical exam or laboratory finding), symptom, or disease, temporally associated with the subject's participation in the research, whether or not considered related to the subject's participation in the research.

*Serious Adverse Event (SAE)* is any adverse event that

- (1) results in death;
- (2) is life-threatening;
- (3) results in subject hospitalization or prolongation of existing hospitalization;
- (4) results in a persistent or significant disability/incapacity;
- (5) results in a congenital anomaly/birth defect;
- (6) based upon appropriate medical judgment, may jeopardize the subject's health and may require medical or surgical intervention to prevent one of the other outcomes listed in this definition (examples of such events include allergic bronchospasm requiring intensive treatment in the emergency room or at home, blood dyscrasias or convulsions that do not result in inpatient hospitalization, or the development of drug dependency or drug abuse).

*Life-threatening* means that the event places the subject at immediate risk of death from the event as it occurred.

*Unanticipated Problem* is defined as an event, experience or outcome that meets **all three** of the following criteria:

- is unexpected; AND
- is related or possibly related to participation in the research; AND
- suggests that the research places subjects or others at a greater risk of harm (including physical, psychological, economic, or social harm) than was previously known or recognized.

*Possibly related* means there is a reasonable possibility that the incident, experience, or outcome may have been caused by the procedures involved in the research

*Unexpected* means the nature, severity, or frequency of the event is not consistent with either:

- the known or foreseeable risk of adverse events associated with the procedures involved in the research that are described in (a) the protocol-related documents, such as the IRB-approved research protocol, any applicable investigator brochure, and the current IRB-approved informed consent document, and (b) other relevant sources of information, such as product labeling and package inserts; or
- the expected natural progression of any underlying disease, disorder, or condition of the subject(s) experiencing the adverse event and the subject's predisposing risk factor profile for the adverse event.

## 10.2 Safety Review

[name] or [name] will interview the subjects before their next exposure each week for any adverse events including erythema or any other skin reactions as shown in the table. At the time of the evaluation, it will be determined whether the subject will continue with the next exposure or whether the subject will be removed from the study. This will be based on the determination of the degree of erythema or adverse skin reaction. [name] will serve as an Independent Scientific Reviewer (ISR). He will provide an assurance that the findings and conclusions reached are supported by the data presented, and also, to assure that the content is consistent with applicable scientific standards and will be responsible for a review of the data analysis, data interpretation and/or presentations and manuscripts.

The following known side effects of UVB will be monitored:

Side effect	Signs/symptoms	Instruction for subjects on monitoring
Sunburn	Pain, tenderness of the skin, redness, tightness, itching, and rarely blistering	Check for pain and redness 4-6 hours after treatment. If there is severe pain, should seek medical attention.  If there are blisters, should seek medical attention
Photoaging	Atrophic skin, coarseness, fibrotic areas, increased fragility, laxity, mottled pigmentation, telangiectasias, wrinkling	If there is increased fragility (i.e. easy bruising or tearing of skin), then should seek medical attention. The other photoaging side effects are benign and more of a cosmetic nature.
Tanning	Skin darkening	As a benign side effect, no subject monitoring is needed

In addition, Prior to each treatment, Solius software will prompt the user with the following questions to assess erythema:

1. *Did you observe any pinkness (similar to sunburn) after your last treatment? (yes / no)*
2. *Did the pinkness last for more than 3 days? (yes / no)*
3. *Did you experience any pain or discomfort (excluding itch) with the pinkness? (none / mild / moderate/severe)*

Based on the user's response, the software could maintain current dose, reduce dose, or block account for further investigation. The PI or [name] or [name] will be notified to perform further assessment if an account was blocked by the software.

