#### **4.1.1 Endpoint Measures**

1. At each visit, the subjects will be asked to report any adverse events and any skin changes. These adverse events will be tabulated and reported at the study completion.
2. Blood samples will be obtained from all subjects at baseline (prior to the first titration, week 2), prior to the intervention (week 6) and end of the study. Blood samples will be sent to the Quest Diagnostics or to the Boston Medical Center's clinical laboratory for determining the serum 25(OH)D levels.

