**Table 2. Outcomes measurement at each time point of the study for both study groups**

Activity	Baseline Wk 1	Titration					Intervention			
		Wk 2	Wk 3	Wk 4	Wk 5	Wk 6	Wk 7	Wk 8	Wk 9	Wk 10
Informed Consent	X									
Inclusion/Exclusion	X									
Medical History	X									
Demographics/ Skin typing	X									
UVB Exposure		X	X	X	X	X	X	X	X	X
25(OH)D	X	X					X			X
Sun exposure/ Vit. D food checklist	X	X								X
Concomitant Medications	X	X					X	X	X	X
Adverse Events		X					X	X	X	X

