The subject's dosage will be administered under conditions of full-body exposure (males in swimming trunks or briefs and females in bikini or bra and panties) of 0.6 minimal erythema dose (MED) once per week for 4 weeks. At each visit, the subject will report adverse events and any skin changes.

We will have the blood samples drawn by trained professionals to minimize the risk of hematoma formation, bleeding, or infection at the site of needle insertion. Study staff will update subjects in a timely way on any new information that may affect their health, welfare, or decision to stay in this study. Any and all side effects reported will be recorded in the subjects' file in the study binder. Subjects will be instructed to call the study staff or PI immediately if any side effects do occur. The PI will advise the subjects according to the symptoms reported. After the determination, all samples will be de-identified. The PI will be available to answer any questions or concerns from potential subjects prior to consenting. We have a plan to protect subject privacy and confidentiality, which is explained in the plan to protect subject privacy and confidentiality in the data section.

Vitamin D deficiency and insufficiency is common in adults due to an inadequate dietary intake of vitamin D and or inadequate sun exposure. Chronic vitamin D deficiency and insufficiency can lead to bone loss resulting in increased risk of fracture later in life. Chronic vitamin D deficiency can also cause a mineralization defect of the skeleton resulting in osteomalacia. Short term (10 weeks) vitamin D deficiency and insufficiency is not associated with significant bone loss or osteomalacia. Therefore, the participants are at no increased risk for fracture or osteomalacia. At the termination of this study those participants will be encouraged to take a vitamin D supplement along the guidelines recommended by the Endocrine Society to correct their vitamin D deficiency and insufficiency.

Chronic excessive exposure to sunlight or ultraviolet radiation for prolonged periods of time, in years or decades, can increase risk for nonmelanoma skin cancer. To minimize the risk the subjects will be 22 years and older and will be exposed to suberythemal doses of UVB radiation for the duration of the study

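### No adverse event enquiry is scheduled after the Wk 10 exposure, so delayed reactions to the last exposure are recorded only if the subject reports them unprompted

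*Combined protocol and SAP*

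**What the plan says.** Adverse events are sought by three scheduled routes.

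- **Staff interview (Section 10.2).** Study personnel "will interview the subjects before their next exposure each week for any adverse events including erythema or any other skin reactions". The interview informs the decision on whether the subject goes on to that next exposure.
- **Software questions (Section 10.2).** These are put before each treatment and concern the one before it: "Did you observe any pinkness (similar to sunburn) after your last treatment" and "Did the pinkness last for more than 3 days", followed by a question on pain or discomfort.
- **Visit enquiry (Sections 4.1.1 and 6.3).** "At each visit, the subjects will be asked to report any adverse events and any skin changes". Section 6.3 adds questioning and examination at every exposure.

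The results are an endpoint measure: "These adverse events will be tabulated and reported at the study completion" (Section 4.1.1).

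Outside the visits, two provisions rely on the subject. The side-effect table in Section 10.2 instructs: "Check for pain and redness 4-6 hours after treatment", with medical attention to be sought for severe pain or blisters. Section 6.1 adds: "Subjects will be instructed to call the study staff or PI immediately if any side effects do occur".

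Table 2 marks UVB exposure in every week from Wk 2 to Wk 10 and has no later column. The payment table in Section 6.2 also ends at Wk 10. Sections 2 and 9 give participation as 10 weeks: one for screening, five for titration and four for treatment.

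**The concern.** The weekly interview and the software questions each ask about the preceding exposure, and each depends on there being another one. After Wk 10 there is none. Table 2 marks adverse events at Wk 10, but an enquiry that day comes too soon for the reactions the protocol itself watches for: redness some hours after treatment, and pinkness that persists for days.

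Safety is a stated objective in Section 2, and Section 3.2 presents the study as preparation for a larger one on safety and efficacy. As written, the tabulation would combine prompted reports for the earlier exposures with unprompted reports for the last. The events most likely to be lost are mild ones, which a subject would mention when asked but would not telephone about.

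**Working it through.** **1. Reproduce the schedule.** Sections 2 and 9 give 1 + 5 + 4 = 10 weeks. Table 2 marks exposures at Wk 2 to Wk 10, which is 5 + 4 = 9. The payment table agrees on the number of visits: transport of up to $300 at $30 per visit is 300/30 = 10 visits, Wk 1 to Wk 10. Nine exposures is a maximum, because Sections 6.1 and 8 describe titration as lasting up to five weeks.

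**2. Count exposures followed by a scheduled enquiry.** Count an exposure as covered if a later scheduled visit exists at which Sections 4.1.1 and 10.2 call for enquiry.

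- Covered: Wk 2 to Wk 9, 8 of 9. Not covered: Wk 10, 1 of 9.
- Treatment period: Wk 7, 8 and 9 covered; Wk 10 not, 1 of 4.
- If 10 subjects complete: 10 of 90 subject-exposures, and 10 of 40 in treatment.
- If 8 complete (the number Section 12.3 expects at the end): 8 of 72, and 8 of 32.

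**3. Check for a later visit.** Section 2 places the last blood sample after the end of the study, and the payment table shows an unexplained double blood draw at Wk 10. Either could hint at a later visit. However, Table 2 puts the final 25(OH)D sample at Wk 10, transport covers exactly ten visits, and no adverse event enquiry is attached to a later draw.

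**4. What the documents say about risk.** Section 3.1 reports an earlier cohort study of the device in which six subjects had four weekly exposures at 0.75 MED, with no adverse events: 0 in 6 × 4 = 24 exposures. Treating exposures as independent, the exact one-sided 95% upper bound is 1 − 0.05^(1/24) = 11.7%. This is only a guide. The study was small and limited to skin types I to III, and the documents do not say how events were sought after its last exposure.

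**5. Expected last-exposure reactions.** Let p be the risk per treatment exposure, an assumption taken from 0 to 10%. Section 10.4 withdraws a subject who has an adverse reaction to the light source, so a subject reaches the fourth treatment exposure only without a reaction to the first three. In 10 subjects the expected number reacting to the last exposure is 10 × p × (1 − p)^3.

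| p | Expected number in 10 subjects |
|---|---|
| 0 | 0 |
| 1% | 10 × 0.01 × 0.99^3 = 0.10 |
| 2% | 10 × 0.02 × 0.98^3 = 0.19 |
| 10% | 10 × 0.10 × 0.90^3 = 0.73 |

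These are counts before allowing for calls. Every reaction that a subject phones in reduces the number missed.

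**The case against.** The strongest reply is that the plan already handles what matters. Subjects are told to inspect their skin after treatment, to seek medical attention for severe pain or blisters, and to call about any side effect; Section 6.1 says that reported side effects are recorded. The weekly interview exists to decide on the next exposure, so its absence after the last one is not a contradiction. Section 12 contains no safety analysis that could be biased, and reactions to treatment exposures are still asked about after Wk 7, 8 and 9. All of this stands. It confines the gap to mild, unreported reactions to one exposure, but it does not supply a prompted enquiry about that exposure.

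A reader might go further and infer that 1 in 9, or 1 in 4, of all reactions will be missed. The documents do not support that. Those fractions count exposures, not events. They would carry over to events only if risk were equal at every exposure and nobody called. Under Sections 6.1 and 8, titration escalates until a maximum or a skin reaction, so reactions are anticipated there, whereas the treatment exposure is set to avoid redness.

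A reader might also infer that any later contact must fall outside the stated 10 weeks. That is not settled. If the Wk 1 visit is day 0, the Wk 10 visit is day 63 and ten full weeks end on day 70, so a call 4 to 7 days later (days 67 to 70) would fit.

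Finally, the Study Visit Report Form named in Section 11.3 and the consent pages were not available for this review. Either could contain a follow-up contact.

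**Conclusion.** The gap is real and minor. In the protocol text, no adverse event enquiry is scheduled after the final exposure, so delayed reactions to it enter the Section 4.1.1 tabulation only through unprompted reporting. One of up to nine scheduled exposures per subject is affected, and one of four in treatment.

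At assumed risks of 0 to 10% per exposure, about 0 to 0.7 last-exposure reactions are expected in 10 subjects (about 0.1 to 0.2 at 1 to 2%), before allowing for calls. This assumes that 10 subjects start treatment, that risk is the same at each treatment exposure and across subjects, and that a treatment reaction leads to withdrawal. Without withdrawal, the figure at 10% would be 10 × 0.10 = 1.0. If subjects differ in susceptibility, those who reach the last exposure are the less reactive ones, and the count would be lower. The consequence is limited to the completeness of a descriptive safety listing; the 25(OH)D analysis is unaffected.

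**What to change.** Add to Sections 9 and 10.2, and as an entry in Table 2, one telephone contact by existing staff about 7 days after each subject's last exposure and no earlier than day 4. Day 4 is the earliest point at which the question on pinkness beyond three days can be answered; about 7 days matches the recall interval of the earlier exposures. Use the same adverse event interview and the same three erythema questions, and include the answers in the Section 4.1.1 tabulation.

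For a subject who ends early, Section 9 already requires a final blood sample. The call is needed only if that draw does not fall at least 4 days after the last exposure; otherwise the questions can be asked at the draw.

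The cost is about 10 short calls, with no extra clinic visit, and an amendment submitted to the IRB under Section 13. If the contact falls outside the 10 weeks as the sponsor counts them, the participation statements in Sections 2 and 9 need a matching edit. If the Study Visit Report Form or the consent form already provides for such a contact, it is enough to state it in the protocol.

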### 10.3 Reporting Plans

The Principal Investigator at BMC/BU Medical Campus will report Unanticipated Problems, safety monitors' reports, and Adverse Events to the BMC/BU Medical Center IRB in accordance with IRB policies:

- Unanticipated Problems occurring at BMC/BU Medical Campus involving a fatal or life-threatening event will be reported to the IRB within 2 days of the investigator learning of the event.
- Unanticipated Problems occurring at BMC/BU Medical Campus not involving a fatal or life-threatening event will be reported to the IRB within 7 days of the investigator learning of the event.
- Reports from safety monitors with recommended changes will be reported to the IRB within 7 days of the investigator receiving the report.
- Adverse Events (including Serious Adverse Events) will be reported in summary at the time of continuing review, along with a statement that the pattern of adverse events, in total, does not suggest that the research places subjects or others at a greater risk of harm than was previously known.
- Reports from safety monitors with no recommended changes will be reported to the IRB at the time of continuing review.

### 10.4 Stopping Rules

A subject will be withdrawn from the study if refuse to participate, or if subject's serum 25(OH)D level is more than 100 ng/mL, or if the subject undergoes an adverse reaction to the light source e.g. skin erythema or pruritus.

## 11 Data Handling and Record Keeping

### 11.1 Confidentiality

Subjects are assigned a code after consent and enrolled in the study. All coded records containing subject information will be stored in [name] offices under lock and key. The blood samples will be kept in the [name] lab (M-1011). The door to the Vitamin D lab is accessed by those who have ID access to the lab.

The data will be coded and after 7 years will be deidentified and kept indefinitely. Electronic information will be stored on a departmental server ("Y"drive) and "C" drive of study coordinator's computer both of which are password protected. Paper records will be stored in a locked room for which only study staff will have access to. Master list will be stored on the study coordinator's PC and will not be stored with study data. All other electronic data will be on the PC of the study coordinator, which is password protected. Paper master list will be stored and locked in M1013; only study staff and study coordinator have access to this room. All locations where data will be kept are inaccessible to the public. Data will be available only to study personnel. Data will be kept in a locked room. Study code will be used for all study data that is collected. The study coordinator and study staff will keep the subject list on their computer, which is password accessible only.

The study monitor or other authorized representatives of the sponsor may inspect all documents and records required to be maintained by the investigator, including but not limited to, medical records (office, clinic, or hospital) and pharmacy records for the subjects in this study. The clinical study site will permit access to such records.

## 11.2 Source Documents

Data generated by the methods described in the protocol will be recorded in the subjects' medical records and/or study progress notes. Data may be transcribed legibly on CRFs supplied for each subject or directly inputted into an electronic system or any combination thereof.

## 11.3 Case Report Forms

The study case report form (CRF) will be the primary data collection instrument for the study. All data requested on the CRF will be recorded. All missing data will be explained. If a space on the CRF is left blank because the procedure was not done or the question was not asked, "N/D" will be written. If the item is not applicable to the individual case, "N/A" will be written. All entries will be printed legibly in black ink. If any entry error has been made, to correct such an error, a single straight line will be drawn through the incorrect entry and the correct data will be entered above it. All such changes will be initialed and dated. There will be no erasures or white-out on CRFs. For clarification of illegible or uncertain entries, the clarification will be printed above the item, then initialed and dated.

See the Appendix for the following CRFs: Study Visit Report Form

## 11.4 Study Records Retention

All coded records containing subject information will be stored in [name] offices under lock and key. The blood will be kept in the [name] lab (M-1021A). The door to the Vitamin D lab is accessed by those who have ID access to the lab. The blood samples and data will be de-identified and kept indefinitely. They may be used for possible additional research in the future. Electronic information will be stored on a departmental server ("Y"drive) and "C" drive of study coordinator's computer both of which are password protected. Paper records will be stored in a locked room for which only study staff will have access to. Master list will be stored on the study coordinator's PC and will not be stored with study data. All other electronic data will be on the PC of the study coordinator, which is password protected. Paper master list will be stored and locked in M1013; only study staff and study coordinator have access to this room. All locations where data will be kept are inaccessible to the public. Data will be available only to study

personnel. Data will be kept in a locked room. Study code will be used for all study data that is collected. The study coordinator and study staff will keep the subject list on their computer, which is password accessible only. Study records will be retained for at least seven years after completion of the study. Documentation of informed consent of subjects will be retained for at least seven years after the study is closed, unless the IRB waived the requirement for informed consent or documentation of informed consent. Such records may be preserved in hardcopy, electronic or other media forms and must be accessible for inspection and copying by authorized individuals.

## 12 Statistical Plan

### 12.1 Statistical analysis

Data will be analyzed using the statistical software package SPSS (SPSS Institute, Chicago, USA). Serum levels of 25(OH)D will inspect for normal distribution using the Kolmogorov-Smirnov test, homogeneity of the variance (Levene-test), and outliers. The results will present as mean±standard deviation, or median.

Serum levels of 25(OH)D will be compared before and after the study using the paired Student's t-test (for normal distribution) or Wilcoxon test for repeated measures. Also, controlling for putative confounders such as skin type and sex, we will employ univariate general linear models (GLM) for the 25(OH)D levels. Significant P-value will consider <0.05.

### 12.2 Study Hypotheses

We expect that with the incorporation of a 4-week phototherapy regimen, subjects will increase their serum 25(OH)D levels. In particular, we expect individuals with Fitzpatrick Type I and II skin to show the greatest response to phototherapy.

